#### 10.3.2 Day 2-12 Treatment Phase and Clinic Visits

##### Group 1

- Participants will attend the clinic every third day (Days 4, 7 and 10).
- A targeted physical exam (See [Section 11.11](#)) will be performed within 1 hour prior to dose administration on Days 4, 7 and 10
- Vital signs will be performed within 1 hour prior to dose administration on Days 4, 7 and 10
- Blood collection for hematology and coagulation markers (PT, APTT, INR), collection of serum for chemistry will be performed within 1 hour prior to dose administration on Days 4 and 7
- Blood samples for investigational drug detection and anti-drug antibodies will be collected any time prior to drug administration on Days 4 and 7.
- Study drug will be administered under supervision in the clinic by intranasal delivery into each nostril every third day (Days 4, 7 and 10) using the Aptar Unidose device.
- A nasal examination will be performed 3 hours after drug administration on Day 4, 7 and 10
- A COVID-19 RAT test will be performed before dosing on Day 4, 7 and 10.
- A Sino-Nasal Outcome Test on will be performed on Day 7 at 2 hours after drug administration.
- Intranasal MLF samples will be collected prior to dosing on Day 4 and Day 7.
- Subject diaries will be reviewed by study staff at each clinic visit.
- Record solicited AEs and unsolicited AEs/SAEs daily
- Record concomitant medication use daily

**Group 2**

Participants will attend the clinic every other day (Days 3, 5, 7, 9 and 11).

- A targeted physical exam will be performed within 1 hour prior to dosing on Days 3, 7 and 11.
- Vital signs will be assessed within 1 hour prior to dosing on Days 3, 7 and 11.
- Blood collection for hematology and coagulation markers (PT, APTT, INR), collection of serum for chemistry within 1 hour prior to dosing on Days 3 and 7.
- Blood samples for investigational drug detection and anti-drug antibodies will be collected on Day 3 and Day 7, any time prior to drug administration.
- Study drug will be administered under supervision in the clinic by intranasal delivery into each nostril every other day (Days 3, 5, 7, 9 and 11) using the Aptar Unidose device.
- A nasal examination will be performed 3 hours after drug administration on Day 3, 7 and 11.
- A COVID-19 RAT test will be performed before dosing on Day 3, 7 and 11.
- A Sino-Nasal Outcome Test on will be performed on Day 7 at 2 hours ( $\pm 15$  mins) post-dose.
- Intranasal MLF samples will be collected prior to dosing on Day 3 and Day 7.
- Subject diaries will be reviewed by study staff at each clinic visit.
- Record solicited AEs and unsolicited AEs/SAEs daily
- Record concomitant medication use daily

**Group 3**

- Participants will attend the clinic daily (Days 2-12).
- A targeted physical exam will be performed within 1 hour prior to dosing on Days 3, 7 and 11.
- Vital signs will be assessed within 1 hour prior to dosing on Days 3, 7 and 11.
- Blood collection for hematology and coagulation markers (PT, APTT, INR), collection of serum for chemistry within 1 hour prior to dosing on Days 3 and 7.
- Blood samples for investigational drug detection and anti-drug antibodies will be collected on Day 3 and Day 7, any time prior to drug administration.
- Study drug will be administered under supervision in the clinic by intranasal delivery into each nostril daily (Days 2-12) using the Aptar Unidose device.
- A nasal examination will be performed 3 hours after drug administration on Day 3, 7 and 11.
- A COVID-19 RAT test will be performed before dosing on Day 3, 7 and 11.
- A Sino-Nasal Outcome Test on will be performed on Day 7 at 2 hours ( $\pm 15$  mins) post-dose.
- Intranasal MLF samples will be collected prior to dosing on Day 3 and Day 7.
- Subject diaries will be reviewed by study staff at each clinic visit.
- Record solicited AEs and unsolicited AEs/SAEs daily
- Record concomitant medication use daily

**10.3.3 Day 14 Follow-up visit**

Participants will attend the research unit on Day 14 and the following procedures will take place:

- Recording concomitant medications

- A COVID-19 RAT test
- Targeted physical examination
- Vital signs
- Collect whole blood for hematology
- Collect serum for chemistry
- Collect blood for PT, APTT, INR
- Collect serum for drug concentrations
- Collect serum for anti-drug antibodies
- Collect nasal mucosal lining fluid (MLF) sample
- Perform Sino-Nasal Outcome Test
- Review diary
- Record AEs/SAEs

#### 10.3.4 Days 15-17

Solicited and unsolicited AEs/SAEs and concomitant medications will be recorded daily using the participant diary

#### 10.3.5 Day 28 End of Study Visit

Participants will come into the research unit on Day 28 and the following procedures will take place:

- Recording concomitant medications
- Vital signs
- Twelve-lead ECG
- Perform Sino-Nasal Outcome Test
- Collect whole blood for hematology
- Collect serum for chemistry
- Collect blood for PT, APTT, INR
- Collect urine for urinalysis
- Record AEs/SAEs
- Review and collect diary
- Urine pregnancy test (females of child-bearing potential only)

## 11 STUDY PROCEDURES

For the exact timing of each procedure, please refer to the study SoA (refer to [Appendix 1](#), [Appendix 2](#) and [Appendix 3](#)). Clinical staff are required to perform assessments at the nominated timepoints within the time windows indicated in the SoA. Actual times of procedures for each participant may vary depending on scheduling and will be recorded in the eCRF. In the event of multiple procedures scheduled at the same time, the order, where possible, will be (1) vital signs, (2) 12-lead ECG, (3) PK/PDc sampling (4) safety laboratory blood sampling (5) all other procedures.

Where required, the timing of post-dose procedures will be in reference to administration of the last actuation completed.

### 11.1 Informed Consent

The Information and Informed Consent Form (ICF) will be provided to participants at

---

Screening and signed prior to any study procedures being performed. Investigators at each site are responsible for maintaining a record of all participants consented, including both those who enter the study and those who do not.

## **11.2 Demographics**

Demographic information collected will include age, sex, race, and ethnicity. Where local regulations do not permit certain demographic data to be collected, collection of those data will not be required.

## **11.3 Medical and Surgical History**

A full medical history will be obtained at Screening (to be updated on Day 1, prior to dose administration), including medication history and drug allergies. Medical history can be obtained through participant interview and medical records.

All findings will be recorded on the Medical History eCRF.

## **11.4 Prior and Concomitant Medications and Therapies**

All medications and therapies administered to participants between signing the ICF and the final follow up visit will be recorded in the participant's eCRF. The name, dose, route of administration, dosing schedule, indication and start and stop dates of all medications and therapies must be recorded. Dates of changes to medications (commencement, cessation and/or alteration in dose or schedule) should also be recorded. Medications include prescription and over the counter medications (including herbal products, vitamins, nutritional supplements). For participants entering on a stable dose of permitted medication, any change in dose should also be recorded.

## **11.5 Height and Weight**

Body height (centimetres) and weight (kilograms) will be measured, and body mass index (BMI) will be calculated. Height should ideally be measured on a wall-mounted stadiometer. Weight should be measured in light-weight clothing, without shoes.

## **11.6 COVID-19 Rapid Antigen Test**

A COVID-19 rapid antigen test (RAT) will be performed at the timepoints indicated in the schedule of assessments. Participants who return a positive result will be withdrawn from the study.

## **11.7 Follicle-Stimulating Hormone**

Female participants who report as postmenopausal (where postmenopausal is defined as no menses for 12 months without an alternative medical cause) will have a serum FSH test at screening. If serum FSH levels are below the cut-off limit as defined by the local testing laboratory, participants will be considered to be of childbearing potential and will be required to use appropriate contraception for the duration of the study.

## **11.8 Pregnancy Test**

Female participants of child-bearing potential will have a serum hCG pregnancy test during Screening. A urine hCG pregnancy test will be conducted on Day 1 as per the SoA. If any of

the urine hCG tests are positive, pregnancy will be confirmed by a serum hCG test. In instances of a positive pregnancy result at any time point, the participant will be withdrawn from the study. Participants withdrawn from the study due to pregnancy may be replaced at the discretion of the PI. Refer to Section [12.7](#) for pregnancy reporting guidelines.

### **11.9 Serology**

HIV antibody, HBsAg, and HCV antibody will be measured at screening. Participants with a positive result will not be eligible to participate in the study. Investigators must ensure compliance with local governing legislation and reporting requirements associated with communicable diseases.

### **11.10 Clinical Laboratory Assessments**

Blood samples will be collected for haematology, clinical chemistry and coagulation safety assessments; urine samples will be collected for urinalysis, and urine drugs of abuse testing. An alcohol breath test will be performed as indicated in the schedule of assessment for each study part.

Tests performed by the local laboratory are described in [Appendix 5](#). All abnormal assessments assessed as clinically significant (CS) by the PI will be repeated. Abnormal assessments that are not CS may be repeated at discretion of the PI. Note: Any deviation in laboratory values that are confirmed on re-examination to be CS and (in the opinion of the PI or medically qualified nominee) would jeopardise the safety of the participant or impact on the validity of the study results), will result in exclusion/withdrawal of that participant.

All safety laboratory assessments will be assessed by a certified local laboratory, using that laboratory's normal ranges. The Investigator must review the laboratory report, document this review, and record any CS changes occurring during the study in the AE section of the eCRF.

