## 6.5 Participant Withdrawal Criteria

Participants will be advised that they are free to withdraw from the study at any time for any reason or, if necessary, the PI (or delegate) may discontinue a participant from the study to protect the participant's health. A participant may voluntarily withdraw or be withdrawn from the study for reasons including, but not limited to, the following:

- The need to take medication which may interfere with study measurements.
- Intolerable/unacceptable AEs.
- Positive test for Covid-19
- Noncompliance of the participant with the protocol.
- Withdrawal of consent; or
- If, in the PI's (or delegate's) judgement, it is in the participant's best interest.

The Sponsor will be notified as soon as possible of any participant withdrawals. The date and reasons for withdrawal will be recorded in the eCRF and included in the final clinical study report, along with any AEs and necessary medical treatment (up until the point of study withdrawal).

Any participant who prematurely discontinues study drug, should have, if possible, all scheduled safety assessments performed, including all follow-up visit assessments as scheduled. If a participant withdraws from the study, an attempt should be made to collect all remaining safety samples scheduled for that day.

In the event that a participant is discontinued from the study due to an SAE, the PI (or delegate), or medically trained nominee, will evaluate the urgency of the event. If the situation warrants, the PI (or delegate), or medically trained nominee, will take appropriate diagnostic and therapeutic measures and attempt to notify the sponsor's medical expert. If the situation is not an immediate emergency, the PI (or delegate), or medically trained nominee, at the clinical facility will attempt to contact the sponsor's medical expert for consultation. No medical help, diagnosis, or advice will be withheld from the participant due to an inability to contact the sponsor's medical expert. The participant will be encouraged to remain available for follow-up medical monitoring.

Participants who withdraw from the study prior to treatment will be replaced according to recruitment and enrolment processes outlined in [Section 7.3](#).

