**Figure 8-A Unidose Nasal Device**

Each Unidose nasal device delivers a dose of 25 mg. Detailed instructions are provided in the study Pharmacy Manual.

The total dose to be delivered will be divided equally across both nostrils, with a total of 1 actuation per nostril required for each dose, i.e., a total dose of 50 mg (See [Table 8-A](#)).

All dosing will take place in the clinical facility under the supervision of site staff.

Participants in study Part A (sentinel cohort) will be observed as in-patients for 24 hours after administration of study drug.

Participants in study Part B (multiple dose cohort) will be observed on site for 4 hours after administration of the first dose.

- Participants in Group 1 will return to the site every 3rd day (Days 4, 7 and 10) for dosing and safety monitoring
- Participants in Group 2 will return to the site every 2nd day (Days 3, 5, 7, 9 and 11) for dosing and safety monitoring
- Participants in Group 3 will return to the site daily (Days 2 to 12) for dosing and safety monitoring

Details of dose administration will be recorded in the eCRF.

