### 12.3 Procedures and Time Period for Detecting Adverse Events

The Investigator or designee is responsible for detection, recording and reporting of events that meet the criteria and definition of AEs.

As a consistent method of soliciting AEs, the participant shall be asked a nonleading question such as: "How do you feel?".

The presence or absence following 'solicited AEs' will be assessed by direct questioning:

- stuffy nose
- runny nose
- sneezing
- nasal irritation
- nasal tenderness/ pain
- loss of smell
- sore throat/ scratchy throat
- cough

Detection and recording of study related AEs and SAEs extends from the signing of the consent form until completion of the last study related procedure (including follow-up for safety assessments). Any AE reported or observed at or after the start of dosing with study drug will be recorded as a treatment-emergent AE (TEAE) or SAE.

Any pre-existing conditions or signs and/or symptoms present in a participant prior to the start of the study (i.e., before informed consent), should be recorded as medical history. In addition, any change in health status that is reported or observed after informed consent but prior to starting study drug and is deemed by the study Investigator to be "not related" to study procedures, will be documented as medical history.

A post-study AE/SAE is defined as any event that occurs outside of the nominal AE/SAE study detection period. Investigators are not obligated to actively seek AEs/SAEs in former study participants. However, if the Investigator learns of any SAE, including a death, at any time after a participant has completed the study and he/she considers the event reasonably related to the investigational product, the Investigator will promptly notify the Sponsor.

Participants must be provided with an “Emergency Wallet Card” indicating the name of the investigational product, the study number, the Investigator’s name, a 24-hour emergency contact number, and, if applicable, excluded concomitant medications.

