## 12.6 Follow-up of Adverse Events and Serious Adverse Events

After the initial AE/SAE report, the Investigator is required to proactively follow each participant and provide further information to the Sponsor on the participant's condition.

All AEs and SAEs documented at a previous visit/contact that are designated as ongoing, will be reviewed at subsequent visits/contacts. If these have resolved, this should be documented. AEs/SAEs that have not resolved by the end of the study, or that have not resolved upon discontinuation of the participant's participation in the study, must be followed until any of the following occurs:

- The event resolves.
- The event stabilises.
- The event returns to Baseline, if a Baseline value is available.
- The event can be attributed to agents other than the study drug or to factors unrelated to study conduct.
- It becomes unlikely that any additional information can be obtained (participant or health care practitioner refusal to provide additional information, lost to follow-up after demonstration of due diligence with follow-up efforts).

The Investigator will ensure that AE/SAE follow-up includes any supplemental investigations as may be indicated to elucidate the nature and/or causality of the event. This may include additional laboratory tests or investigations, histopathological examinations, or consultation with other health care professionals.

The Sponsor may request that the Investigator perform or arrange for the conduct of supplemental measurements and/or evaluations to elucidate as fully as possible the nature and/or causality of the AE/SAE. If a participant dies during participation in the study or during a recognised follow-up period, where possible, the Sponsor will be provided with a copy of any post-mortem findings, including histopathology.

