### *13.7.5 Clinical Laboratory Safety Data*

Clinical laboratory safety data will be summarised by laboratory parameter. Observed values and changes from baseline for continuous clinical laboratory parameters will be summarised at each scheduled timepoint using descriptive statistics. Categorical clinical laboratory data will be summarised at each scheduled timepoint using participant counts and percentages. The clinical assessment of laboratory data will be summarised at each scheduled timepoint using participant counts and percentages. Individual participant profiles will be presented for any laboratory parameters with at least one post-dose value outside the laboratory's reference ranges that is deemed clinically significant.

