The listings of laboratory parameters (haematology, chemistry, coagulation, and urinalysis) will include all the information collected. In addition, the observations that are used as the baseline record (value) for each parameter will be flagged, and the change from baseline values (where applicable) at each scheduled post baseline (scheduled and unscheduled) visit will be presented. In addition, a separate listing will be generated for any individual laboratory results assessed as clinically significant.

These listings will be presented by treatment groups defined in section 4.6, sorted by participant ID and visit for the SS population, along with age, sex, race, and baseline weight of the participant.

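### Protocol 11.10 makes withdrawal mandatory after certain laboratory values without separating stopping drug from leaving the study, so later scheduled safety data can be lost because of a safety outcome

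*Protocol*

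**What the plan says.** Protocol 11.10 covers all laboratory assessments, from screening to end of study. If a deviation is clinically significant on repeat testing and the principal investigator (PI) or a medically qualified nominee considers that it "would jeopardise the safety of the participant or impact on the validity of the study results), will result in exclusion/withdrawal of that participant", the consequence is fixed. The section does not refer to the stopping rules in 6.4.2 or to 6.5.

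Protocol 6.5 sets two levels of follow-up:

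- After stopping drug: "Any participant who prematurely discontinues study drug, should have, if possible, all scheduled safety assessments performed, including all follow-up visit assessments as scheduled".
- After leaving the study: "If a participant withdraws from the study, an attempt should be made to collect all remaining safety samples scheduled for that day".

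The laboratory thresholds in 6.4.2 stop product for all subjects and prompt a review. The individual rule there stops product for that subject. Neither withdraws anyone from the study.

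Several provisions keep the triggering event in view. Under 12.6, events unresolved when a participant ends "participation in the study, must be followed until any of the following occurs", with resolution and stabilisation among the end points. Protocol 13.7.5 adds that "Individual participant profiles will be presented for any laboratory parameters with at least one post-dose value" that is out of range and clinically significant. SAP 13.2 says that "a separate listing will be generated for any individual laboratory results assessed as clinically significant". For new events, however, 12.3 says that "Investigators are not obligated to actively seek AEs/SAEs in former study participants".

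**The concern.** Changes from baseline in laboratory parameters, vital signs, ECG and SNOT-22 are all components of the primary endpoint (Protocol Table 5-A). If 11.10 removes a participant from the study, the later scheduled values of these measures are missing because of a worrying safety result. The by-visit summaries for later visits would then leave out a participant whose course is of particular interest.

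The SAP would not fill the gap. Summary tables use scheduled time points only, unless an unscheduled visit is documented as a replacement (4.2). Missing values are not imputed (4.5). Early-termination data appear in listings only (4.6), and neither schedule of assessments contains an early-termination visit.

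**Working it through.** **Step 1: which kind of withdrawal?** In 11.10 it is the participant, not the product, that is withdrawn. Section 6.5, whose heading concerns participant withdrawal, uses the word for leaving the study, and so do 11.6 (positive antigen test) and 11.8 (pregnancy). When the protocol stops drug, it speaks of discontinuing product or study drug (6.4.2, 6.5). The list of source documents in 14.3 likewise pairs discontinuation with treatment and withdrawal with the study. For a post-dose value, study withdrawal is therefore the most natural reading, though not the only possible one.

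**Step 2: doses left at each post-dose laboratory day.** Part A has one dose, on Day 1, so none remain. In Part B (Protocol 8.5), Group 1 is dosed on Days 1, 4, 7 and 10, and Group 2 on Days 1, 3, 5, 7, 9 and 11. Group 3 is dosed on Day 1 and then: "Participants in Group 3 will return to the site daily (Days 2 to 12) for dosing and safety monitoring". Doses after the laboratory day:

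- Day 3 or 4: 2, 4 and 9 for Groups 1, 2 and 3.
- Day 7: 1, 2 and 5.
- Day 14: 0 in every group.

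**Step 3: check the plan's own count of laboratory time points.** For Part B, Table 11-B budgets 6. Table 21-B gives Screening and Days 1, 3 or 4, 7, 14 and 28, which is also 6. Screening and Day 1 are pre-dose, leaving 6 − 2 = 4 post-dose sets. For Part A, Table 11-A budgets 4, but Table 21-A shows 5 (Screening and Days 1, 2, 8 and 14). Section 6.2 makes Day 14 a telephone contact and 10.2.5 makes it a clinic visit. Both versions are carried below: 3 post-dose sets with a clinic visit, 2 with a telephone contact.

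**Step 4: what one participant can lose under study withdrawal**, assuming it takes effect before the next scheduled visit. Post-dose SNOT-22 is due on Days 1, 7, 14 and 28 in Part B and Days 1 and 8 in Part A. ECG and urinalysis are scheduled only at Screening and End of Study.

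| Trigger | Laboratory sets lost | SNOT-22 lost | Only post-dose ECG and urinalysis |
|---|---|---|---|
| Part B Day 3 or 4 | 3 of 4 | 3 of 4 | lost |
| Part B Day 7 | 2 of 4 | 2 of 4 | lost |
| Part B Day 14 | 1 of 4 | 1 of 4 | lost |
| Part B Day 28 | none | none | kept |
| Part A Day 2 | 2 of 3 (clinic) or 1 of 2 (telephone) | 1 of 2 | lost if clinic |
| Part A Day 8 | 1 of 3 (clinic) or 0 of 2 (telephone) | none | lost if clinic |
| Part A Day 14 | none | none | kept |

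A Part B Day 14 trigger also loses the Day 28 vital signs and up to 28 − 14 = 14 of 28 diary days. If 11.10 means a drug stop, and the 6.5 follow-up is achieved, every loss in the table is zero.

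**Step 5: share of the group.** One case is 1/10 = 10% of a Part B group or 1/5 = 20% of Part A.

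**Step 6: frequency.** The documents give no trigger rate; the 10% in Protocol 13.1 is a hypothetical rate of serious adverse events. For an assumed trigger rate q, the chance of at least one trigger among 35 participants is 1 − (1 − q)^35. This is 30% at q = 1%, 66% at 3%, 83% at 5% and 97% at 10%. These values of q are purely illustrative, and the calculation includes triggers on days when nothing scheduled would be lost.

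**The case against.** The strongest case on the other side has four parts.

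*Wording.* A reader might infer that once no doses remain, 11.10 can only mean leaving the study. The documents do not support that. Sections 11.6 and 11.8 spell out withdrawal from the study, whereas 11.10 does not, and its paired term fits exclusion before dosing and a drug stop during it. With no drug left, it can also be read as leaving nothing to act on. This stands as a possible reading. It leaves a mandatory sentence without effect, however, and does not match how the protocol uses withdrawal elsewhere.

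*Likelihood.* The trigger needs a clinically significant value, confirmation on repeat, and a PI opinion. Once dosing is over, staying in the study means only monitoring visits, so there is little reason to invoke the rule. This stands, and frequency is probably low. But once the opinion is formed, the wording leaves no discretion.

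*Retained signal.* A reader might also infer that the safety signal disappears. It does not:

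- The original triggering value stays in the by-visit summary (SAP 4.2) and the shift tables (SAP 13.2).
- The event is counted in the treatment-emergent tables, including events leading to study withdrawal (SAP 13.1).
- Discontinuation is itself part of the primary endpoint.
- Section 12.6 requires follow-up of the event, with further tests as indicated.
- Section 7.3 may allow a replacement, which can restore group size but not that participant's data.

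All of this stands. What is not protected is the rest of the scheduled assessments and active detection of new events.

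*Consequence.* The safety tables are descriptive, no safety test depends on them, and 6.5 does not forbid later visits. That is correct. It limits the importance of the point but does not remove it.

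**Conclusion.** The concern holds in a limited form. Followed on its most natural post-dose reading, 11.10 can produce outcome-dependent loss of scheduled primary safety data. The loss arises for triggers on Part B Days 3 or 4, 7 and 14 and on Part A Days 2 and 8. For a Part A Day 8 trigger it depends on Day 14 being a clinic visit, as 10.2.5 and Table 21-A have it. Nothing scheduled is lost for a trigger at Part A Day 14 or Part B Day 28, so it would be wrong to infer that every post-dose laboratory day in Part A is affected.

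The sizes above are upper bounds per participant. They assume that withdrawal means leaving the study, that it takes effect before the next visit, and that no later visit is arranged voluntarily. How often this would happen cannot be estimated from the documents. No sample-size figure changes. This is a cheap improvement to the wording rather than a flaw that undermines the trial's safety conclusions.

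**What to change.** Amend 11.10 in two sentences:

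1. A qualifying value found before the first dose leads to exclusion.
2. A qualifying value found after the first dose leads to discontinuation of any remaining study drug. The participant completes all scheduled safety and follow-up assessments where possible, as 6.5 already provides, unless consent is withdrawn or another criterion in 6.5, 11.6 or 11.8 applies.

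The validity ground can stay once follow-up is kept. A bare cross-reference to 6.5 would not be enough, because 6.5 contains both levels of follow-up and 11.10 has to say which one applies.

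The cost is small. The visits are already scheduled, so no procedure is added, though a few would continue off drug. The change may count as a substantial amendment needing ethics committee (HREC) approval under 18.3.
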